5.3.3.1.2 Handling of MLN4924 (Pevonedistat) Specimen(s)

- Process **within 60 minutes** of collection.
- Centrifuge at approximately 1100 to $1300 \times g$ (RCF) for 10 minutes at approximately 4°C in a refrigerated centrifuge. Note: If using a collection device other than Becton-Dickinson, refer to manufacturer's instruction for proper centrifugation force and time.
- Immediately following centrifugation, gently remove plasma from the packed cells and transfer into 2 labeled 2 mL cryovials. Each plasma sample will be split into 2 cryovials, which should be clearly designated as part of "Set 1" (primary set) or "Set 2" (back-up set).
- To ensure a more homogeneous sample, transfer all plasma into one cryovial. From there, split the plasma evenly between the 2 aliquots. A minimum of 0.6 mL needs to be obtained for each aliquot

- Samples being submitted to QPS will be labeled as follows or labeled using the RAVE Specimen Tracking System. Labels generated outside STS should mimic the STS labeling format as shown below:
 - Patient ID: Protocol # (10246) - Treatment ID # (assigned at enrollment) – UPID (assigned in STS)
 - Specimen ID: Protocol # (10246) - UPID plus sequentially generated integer (assigned in STS)
 - Code: PK-PEVO
 - Type: Blood
 - Time Point: pre or post
 - Date/time collected
 - Optional (not included in STS labels): “Set 1” or “Set 2”
- Freeze the plasma samples immediately at approximately -70°C or lower. If a -70°C freezer is not available, freeze and store samples at -20°C. No more than 45 minutes should elapse between blood collection and freezing the plasma sample.
- Store samples frozen at approximately -70°C or lower until shipment.

5.3.3.1.3 Shipping of MLN4952 (Pevonedistat) Sample(s)

- Samples should be stored through the duration of the PK study and shipped as a batch by patient.
- The primary set of samples should be shipped using site supplies to the QPS laboratory within 3 months of first sample's collection date (*i.e.*, if baseline sample is collected on 06/01/2019, all of that patient's samples should be at the QPS laboratory by 09/01/2019). If a second set of patient samples can be batch shipped by waiting up to 2 weeks (*i.e.*, 3.5 months), this is allowed.
- Coordinate shipment with the QPS laboratory (██████████) *via* email prior to shipment (on the day of shipment or before), providing the shipment tracking information and a copy of the sample inventory.
- All samples will be shipped *via* overnight express courier in insulated containers with enough dry ice to maintain the samples in a frozen state for at least 72 hours (3 days), or up to the expected delivery date, whichever is longer.
- Shipments should occur on Monday through Wednesday (Tuesday is the preferred day) except when the following day is a holiday.
- A sample inventory must accompany all shipments.

*Once receipt of the primary set of samples (SET 1) is confirmed by QPS, the back-up set of samples (SET 2) may be shipped.

[REDACTED]

[REDACTED]

5.3.3.1.4 Site Performing MLN4924 (pevonedistat) Correlative Studies

MLN4924 (pevonedistat) PK studies will be conducted by QPS, LLC.

5.3.3.2 Belinostat PK Studies

[REDACTED]

[REDACTED]

- Whenever possible collect PK specimens from a venous access point that has not been used for drug infusion.
- Collect 4-6 mL of venous blood into tubes containing sodium heparin (see tube ordering information below) at the time points specified below for belinostat PK analysis.
- GENTLY invert the tube 8-10 times after collection to avoid sample hemolysis.
- For belinostat, sample collection will occur at these approximate time points on Cycle 1, starting on Day 1, timed from the END of the belinostat infusion:
 - pre-belinostat infusion
 - 5 minutes (± 1 min) prior to the END of belinostat infusion
 - 15 minutes (± 10 min) after the END of the belinostat infusion and then
 - 30 minutes (± 10 min)
 - 1 hr (± 10 min)
 - 2 hrs (± 10 min)
 - 4 hrs (± 10 min)
 - 6 hrs (± 30 min)
 - 8 hrs (± 45 min)
 - and 24 hrs (± 4 hrs) after the END of the belinostat infusion.

Note: if samples cannot be obtained within the stated time point window, it's preferable to draw a sample as close to the time point as possible rather than omitting the sample – be sure the actual time of collection is recorded.

5.3.3.2.1.1 Belinostat PK supply ordering

Each participating site will procure sodium heparin tubes. Recommended items/vendors include:

- BD (Becton Dickinson) Catalog No. 23-021-017 (Manufacturer No. BD 367878): sodium heparin-containing plastic green-top tubes 6 mL
- Fisher Scientific Catalog No. 367878: sodium heparin-containing plastic green-top tubes 6 mL

5.3.3.2.2 Handling of Belinostat PK Specimen(s)

- Centrifuge at 2500-3000 rpm for 10 mins in swinging bucket (SW) or 15 mins in a fixed angle (FA) rotor at 4°C in a refrigerated centrifuge. Make sure that the centrifuge reaches speed and is maintained throughout the entire spin.
- Using a pipette, transfer equal aliquots of plasma into 2 labeled 2 mL cryovials, not exceeding ~1 mL per cryovial. Each plasma sample will be split into 2 cryovials, which should be clearly designated as part of “Set 1” (primary set) or “Set 2” (back-up set).
- Samples being submitted to APC will be labeled as follows or labeled using the RAVE Specimen Tracking System. Labels generated outside STS should mimic the STS labeling format as shown below:
 - Patient ID: Protocol # (10246) - Treatment ID # (assigned at enrollment) – UPID (assigned in STS)
 - Specimen ID: Protocol # (10246) - UPID plus sequentially generated integer (assigned in STS)
 - Code: PK-BELINOSTAT
 - Type: Blood
 - Time Point: pre or post
 - Date/time collected
 - Optional (not included in STS labels): “Set 1” or “Set 2”
- Freeze the plasma samples immediately at approximately ~-70°C or below.
- Store samples frozen at approximately -70°C or lower until shipment.

5.3.3.2.3 Shipping of Belinostat PK Specimen(s)

- Samples should be stored through the duration of the PK study and shipped as a batch by patient (more than one patient/shipment is acceptable if the site has more than one patient on study).
- The primary set of samples should be shipped to the APC laboratory within 3 months of first sample's collection date (*i.e.*, if baseline sample is collected on 06/01/2019, all of that patient's samples should be at the APC laboratory by 09/01/2019). If a second set of patient samples can be batch shipped by waiting up to 2 weeks (*i.e.*, 3.5 months), this deviation is allowed.
- All samples should be shipped *via* overnight express courier in insulated containers with

enough dry ice to maintain the samples in a frozen state.

- [REDACTED]

[REDACTED]

[REDACTED]

[REDACTED]

5.3.3.2.4 Site Performing Correlative Studies

Belinostat PK studies will be conducted by the [REDACTED] under the direction of [name], [REDACTED] is a well-recognized expert in pharmacokinetics who is also a member of the Investigational Drug Steering Committee of NCI/CTEP. She is the director of the APC laboratory. She has published extensively in pharmacokinetic studies of investigational agents, including in rational combination, and performed pharmacokinetic analysis of belinostat in a recently completed CTEP/ET-CTN trial of belinostat in combination with the Wee1 inhibitor AZD1775 in patients with relapsed/refractory AML or high-risk MDS. MLN4924 (pevonedistat) PK studies will be performed by QPS as per Takeda.

Belinostat will be measured in plasma using validated liquid chromatography-tandem mass spectrometry methods (Kiesel *et al.*, 2013; Xu *et al.*, 2012). Plasma concentration versus time data for belinostat and metabolites will be analyzed non-compartmentally or compartmentally using Phoenix WinNonlin. PK parameters for exposure (C_{max} , C_{min} , and AUC) along with $T_{1/2}$ and V_d will be assessed.

[REDACTED]

[REDACTED]

[REDACTED]

[REDACTED]

[REDACTED]

[REDACTED]

5.4.1.1 Collection, Handling, Shipping of PD-WB/FC Specimen(s)

Samples may be collected, handled and shipped in 1 of 2 ways (using the “routine approach” or the “alternative approach”), as shown below. The “routine approach” requires that the samples be immediately processed to mononuclear cell suspensions or pellets at the site where collected, followed by frozen storage and subsequent shipment to VCU CTRL. The “alternative approach” is outlined for sites without capabilities for immediate mononuclear cell isolation and requires that the sample be collected in specialized tubes followed by overnight shipment to VCU CTRL on the day of collection.

5.4.1.2 **Routine Approach** – Collection, Handling, Shipping of PD-WB/FC Specimen(s)

5.4.1.2.1 **Routine Approach** – PD-WB/FC Sample Collection

Paired samples of bone marrow aspirate (optional, from consenting patients) or blood will be collected from all consenting studies when the baseline sample is anticipated to contain $\geq 10\%$ blasts.

Collect paired (pre-treatment and 24 hr post-treatment) samples of either peripheral blood (10 mL) or, optionally from consenting patients, bone marrow aspirate (5 mL) in tubes containing K2-EDTA (see tube ordering information below). The same

sample type (blood or bone marrow aspirate) must be used for both samples.

5.4.1.2.1.1 **Routine Approach** – PD-WB/FC supply ordering

Each participating site will procure K2-EDTA tubes. Recommended items/vendors include:

- BD (Becton Dickinson) Catalog No. 02-689-03 (Manufacturer No. BD367835): K2EDTA-containing plastic lavender-top tubes 3mL
- Fisher Scientific Catalog No. 367835: K2EDTA-containing plastic lavender-top tubes 3mL

5.4.1.2.2 **Routine Approach** – PD-WB/FC Handling of Specimens(s)

Samples will be processed within 2 hours of collection for isolation of leukemic mononuclear cells in a uniform manner, using BD Phosflow lyse/fix red cell lysis buffer (BD Bioscience), by dedicated research personnel according to manufacturer-specified protocol. Briefly, samples will be depleted of red blood cells by incubation with the buffer. After washing and counting, the cells will be resuspended in FBS/10% DMSO solution (5×10^6 cells/mL) in cryovials, frozen using a controlled-rate freezing apparatus or isopropanol chamber, and stored at -80°C .

Samples being submitted to VCU CTRL will be labeled as follows or labeled using the RAVE Specimen Tracking System. Labels generated outside STS should mimic the STS labeling format as shown below:

- Patient ID: Protocol # (10246) - Treatment ID # (assigned at enrollment) – UPID (assigned in STS)
- Specimen ID: Protocol # (10246) - UPID plus sequentially generated integer (assigned in STS)
- Code: PD-WB/FC
- Type: Blood or Bone marrow
- Time Point: pre or post
- Date/time collected
- Additional field for all labels (STS-generated or generated outside STS): Cell count or cell concentration in sample

5.4.1.2.3 **Routine Approach** – PD WB/FC Shipping of Specimen(s)

The frozen cell suspension may be temporarily stored, and then shipped by overnight courier on dry ice to the Clinical and Translational Research Laboratory (CTRL) at the VCU Massey Cancer Center for western blot and/or flow cytometry analysis. Based on preliminary experiments, we have concluded that shipping frozen cell pellets does not adversely affect western blot or flow cytometry results as compared to analyzing fresh samples.

Samples must be paired (baseline samples without post-treatment samples should not be submitted). All complete sample sets for each patient (pre- and post-treatment) must be shipped on dry ice by overnight courier.

If a patient consented to both PD-WB/FC and pharmacogenomic (PG) sampling, the frozen PG cell pellet(s) may be batched for submission to the CTRL along with the frozen pharmacodynamic cell suspensions. A sample inventory must accompany all shipments.

Coordinate shipment and arrival dates with [REDACTED] by phone or email prior to shipment. Plan to ship on Monday through Thursday only. Do not ship samples for arrival on a holiday or weekend. Contact [REDACTED] in advance if any questions arise about timing of shipments.

5.4.1.3 **Alternative Approach** – Collection, Handling, Shipping of PD-WB/FC Specimen(s)

5.4.1.3.1 **Alternative Approach** – PD-WB/FC Sample Collection

Paired samples of bone marrow aspirate (optional, from consenting patients) or blood will be collected from all consenting studies when the baseline sample is anticipated to contain $\geq 10\%$ blasts.

Collect paired (pre-treatment and 24 hr post-treatment) samples of either peripheral blood (10 mL) or, optionally from consenting patients, bone marrow aspirate (5 mL), in Cyto-Chex[®] BCT tube(s) (see tube ordering information below). The same sample type (blood or bone marrow aspirate) must be used for both samples.

5.4.1.3.1.1 **Alternative Approach** – PD-WB/FC supply ordering

As needed, each participating site will procure Cyto-Chex[®] BCT tubes (if opting to use the Alternative Approach to WB/FC sampling). Recommended items/vendors include:

- Streck Catalog No. 213361: Cyto -Chex[®] BCT tubes 5mL (6-tube pack); 25 and 100 tube packs also available from Streck

- Fisher Scientific Catalog No. 11-716-357 (Streck213361): Cyto-Chex[®] BCT tubes 5mL (6-tube pack); 25 tube pack also available from Fisher

5.4.1.3.2 **Alternative Approach** – PD-WB/FC Handling of Specimens(s)

Samples may be held at room temperature until shipment on the day of collection.

Samples being submitted to VCU CTRL will be labeled as follows or labeled using the RAVE Specimen Tracking System. Labels generated outside STS should mimic the STS labeling format as shown below:

- Patient ID: Protocol # (10246) - Treatment ID # (assigned at enrollment) – UPID (assigned in STS)
- Specimen ID: Protocol # (10246) - UPID plus sequentially generated integer (assigned in STS)
- Code: PD-WB/FC
- Type: Blood or Bone marrow
- Time Point: pre or post
- Date/time collected

5.4.1.3.3 **Alternative Approach** – PD-WB/FC Shipping of Specimen(s)

[figure not shown]
Samples will be shipped at room temperature by overnight courier, preferably for morning delivery, to the VCU CTRL laboratory on the day it is collected. The collected samples are stable for up to 48 hours at room temperature (15°C to 30°C) prior to processing.

A sample inventory must accompany all shipments.

Coordinate shipment and arrival dates with [REDACTED] by phone or email prior to shipment. Plan to ship on Monday through Thursday only. Do not ship samples for arrival on a holiday or weekend. Contact [REDACTED] in advance if any questions arise about timing of shipments.

[REDACTED]

5.4.1.4 Site(s) Performing Correlative Studies

5.4.2 Pharmacodynamic Studies (RT-PCR analysis)

See section 5.3.2 for information regarding specimen collection, handling, and shipping, as well as the site performing the correlative study. Sampling for PD-RTPCR analysis is mandatory.

5.4.3 PG Studies

5.4.3.1 Collection of Specimen(s)

- A single baseline sample of bone marrow aspirate (if patient consents to bone marrow sampling) or blood will be collected when the sample is anticipated to contain $\geq 40\%$ blasts.
- Collect a single pre-treatment sample of bone marrow aspirate (2.5 mL) or blood (5 mL) into a tube containing sodium heparin (see tube ordering information below).

5.4.3.1.1 PG supply ordering

Each participating site will procure sodium heparin tubes. Recommended items/vendors include:

- BD (Becton Dickinson) Catalog No. 23-021-017 (Manufacturer No. BD 367878): sodium heparin-containing plastic green-top tubes 6mL
- Fisher Scientific Catalog No. 367878: sodium heparin-containing plastic green-top tubes 6mL

5.4.3.2 Handling of Specimens(s)

Samples will be processed within 2 hours of collection for isolation of leukemic mononuclear cells in a uniform manner using Ficoll-Hypaque by dedicated research personnel according to manufacturer-specified protocol. After washing twice with PBS, 1×10^6 cells/mL will be

aliquoted into one cryovial and remaining cells in another cryovial. Cells will be flash frozen in liquid nitrogen and stored at -80°C as a cell pellet.

Samples being submitted to VCU CTRL will be labeled as follows or labeled using the RAVE Specimen Tracking System. Labels generated outside STS should mimic the STS labeling format as shown below:

- Patient ID: Protocol # (10246) - Treatment ID # (assigned at enrollment) – UPID (assigned in STS)
- Spec ID: Protocol # (10246) - UPID plus sequentially generated integer (assigned in STS)
- Code: PG
- Type: Blood or Bone marrow
- Time Point: pre
- Date/time collected
- Cell count or cell concentration in final cell pellet

5.4.3.3 Shipping of Specimen(s)

The cell pellet(s) may be temporarily stored and then shipped by overnight courier on dry ice to [REDACTED]

[REDACTED] If samples are collected for both PD-WB/FC and PG, the frozen PG cell pellet(s) may be batched for submission to the VCU CTRL along with the frozen PD-WB/FC cell suspensions.

Use shipment instructions from Section 5.3.1.3. A sample inventory must accompany all shipments.

6. TREATMENT PLAN

6.1 Agent Administration

This will be a two-part phase 1 dose-escalation and exploratory dose-expansion study of MLN4924 (pevonedistat) in combination with belinostat. Part A will consist of a 3+3 dose-escalation phase of the combination to assess its safety and tolerability and identify an MTD/tentative RP2D. After the MTD has been established, Part B of the study will involve an exploratory-dose expansion study of 12 additional patients who will be enrolled at the tentative RP2D to gain further insights into the safety of the regimen. MLN4929 (pevonedistat) and belinostat dose rounding is allowed per institutional guidelines.

Treatment will be administered on an outpatient basis. Cycles are to be repeated every 21 days. Reported adverse events and potential risks are described in Section 10. Appropriate dose modifications are described in Section 7. Other than hydroxyurea during the first 5 days of study treatment, no investigational or commercial agents or therapies other than those described below may be administered with the intent to treat the patient's malignancy.

Dose Escalation Schedule				
Dose Level	Belinostat		MLN4924 (pevonedistat)	
	Dose (mg/m²/day)	Administration and Schedule	Dose (mg/m²/day)	Administration and Schedule
-1	800	Intravenously over 30 minutes once daily on Days 1-5 of each 21-day cycle	15	Intravenously over 60 minutes once daily on Days 1, 3, & 5 of each 21-day cycle**
1*	800		20	
2	800		25	
3	800		37	
4	1000		37	
5	1000		50	
6***	1000		59	

* Starting dose level

** When both drugs are given on the same day (Days 1, 3, 5), start the MLN4924 (pevonedistat) infusion within 60 mins after the completion of belinostat infusion.

*** The 59 mg/m² level will not begin until the NCI/CTEP, Principal Investigator and Takeda have closely examined the toxicity, PK and clinical data from the 50 mg/m² cohort. Takeda must give written approval for the 59 mg/m² to begin.

Regimen Description				
Agent	Premedication; Precautions	Dose And Route	Schedule	Cycle Length
Belinostat	See Section 6.4	In 250 mL 0.9% NaCl IV over 30 (± 5 min)*** Dose per assigned dose level.	Days 1-5 (week 1)	21 days (3 weeks)
MLN4924 (pevonedistat)	See Section 6.4	In 250 mL D5W or 0.9% NS IV over 60 min (± 10 min)* Infusion to start within 60 minutes after belinostat infusion ends. Dose per assigned dose level.	Days 1, 3, & 5 (week 1)**	

IV = Intravenously; D5W = dextrose 5% in water; NS = normal saline.

* May extend or interrupt MLN4924 (pevonedistat) infusion as needed for infusion-related reactions, provided total time from drug reconstitution to end of infusion does not exceed 6 hrs (or within 3 hours of coming to room temperature if previously stored for up to 18 hours as shown in Section 6.1.1).

**Doses of MLN4924 (pevonedistat) must be separated by at least 1 full calendar day. When both drugs are given on the same day (Days 1, 3, 5), start the MLN4924 (pevonedistat) infusion within 60 min after the completion of belinostat infusion.

***May extend belinostat infusion to 3 hrs if infusion-related reactions occur.

6.1.1 MLN4924 (pevonedistat)

MLN4924 (pevonedistat) will be given intravenously over 60 minutes (± 10 minutes) through central or peripheral venous access. The IV infusion can be slowed or stopped and restarted for any associated infusion-related reactions. The total time from the IV preparation to end of IV infusion must not exceed 6 hours if stored at room temperature. Alternatively, the prepared IV bag may be stored for up to 18 hours at 2°C to 8°C (36-46°F). After 18 hours of storage at 2°C to 8°C (36-46°F), the prepared IV bag must be used within 3 hours upon coming to room temperature or must be discarded. When both drugs are given on the same day (Days 1, 3, 5), start the MLN4924 (pevonedistat) infusion within 60 min after the completion of belinostat infusion.

6.1.2 Belinostat

Belinostat will be administered IV over 30 minutes (± 5 minutes) by central or peripheral access through an in-line 0.22-micron filter.

Belinostat infusions may be prolonged up to 3 hrs, if deemed necessary, to ameliorate acute infusion-related reactions (nausea, flushing, rhinitis, vomiting, *etc.*) that may occur during, or immediately following infusion. Once diluted in 250 mL of 0.9% sodium chloride, belinostat may be stored at controlled room temperature (20-25°C) for up to 36 hrs, including the infusion time.

6.2 Definition of Dose-Limiting Toxicity

AEs will be assessed according to the NCI Common Terminology Criteria for Adverse Events

(CTCAE), version 5.0. AEs possibly, probably, or definitely related to study drugs will be scored as toxicities.

All participating sites are expected to notify the Principal Investigator and Study Coordinator within 24 hours of awareness that a DLT has occurred.

• [REDACTED]

DLTs will be defined in Cycle 1 as any of the following events that are considered by the investigator to be related to therapy with MLN4924 (pevonedistat) and/or belinostat:

- Any grade 3 or greater non-hematological toxicity that does not recover within 1 week to grade ≤ 1 or baseline with optimal medical management, with the following exception :
 - Grade 3 hypophosphatemia
- Grade 3 or greater ECG QT corrected interval prolonged.
- Grade 3 or greater increased prothrombin time/international normalized ratio (PT/INR) or activated partial thromboplastin time (aPTT) in the absence of anticoagulation therapy.
- Grade 2 or greater elevation of the PT/INR or aPTT that is associated with clinically significant bleeding (CNS, GI, *etc.*).
- Grade 2 or greater increased AST, ALT or bilirubin that persists longer than 2 days between MLN4924 (pevonedistat) doses.
- Delayed initiation of Cycle 2 as follows:
 - More than 2 week delay due to lack of recovery (to $<$ Grade 1 or baseline) from treatment-related non-hematologic toxicity.
 - More than 4 week delay due to lack of recovery (to $<$ Grade 1 or baseline) from treatment-related hematologic toxicity believed not related to leukemic infiltration. Note: Bone marrow evaluation may be required.
- Grade 4 neutropenia or thrombocytopenia extending beyond day 42 in patients with less than 5% blasts in marrow, absence of MDS changes and/or absence of disease by flow cytometry in the marrow.
- Any toxicity that requires discontinuation of either study drug.
- Grade 3 or greater nausea or vomiting despite use of optimal anti-emetic prophylaxis. Optimal anti-emetic prophylaxis is defined as an anti-emetic regimen that employs a 5-hydroxytryptamine 3 serotonin receptor antagonist given in standard doses and according to standard schedules.
- Grade 3 or greater diarrhea that occurs despite maximal supportive therapy
- Grade 3 arthralgia or myalgia despite the use of optimal analgesia
- Other grade 2 or greater MLN4924 (pevonedistat)-related non-hematologic toxicities that, in the opinion of the investigator, require a dose reduction or permanent discontinuation of MLN4924 (pevonedistat).

Note that hematologic toxicities are not DLTs except as noted above.

Only DLTs occurring during Cycle 1 will influence decisions regarding dose escalation, expansion of a dose level, or evaluation of intermediate dose levels. Patients will be monitored through all cycles of therapy for treatment-related toxicities.

Patients who for any reason are not evaluable for DLT will be replaced. See Section 9.3.1 for DLT Evaluable Population.

Management and dose modifications for AEs are outlined in Section 7.

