4.3.3 OPEN/IWRS Questions?

[REDACTED]

[REDACTED]

4.4 **General Guidelines**

Participating sites are required to participate in a protocol-specific Site Initiation Teleconference prior to first patient registration.

Following registration, patients should begin protocol treatment within 7 to 14 business days. Issues

NCI Protocol #: 10246
Version Date: 02/16/2022

that would cause treatment delays should be discussed with the principal investigator. If a patient does not receive protocol therapy following registration, the patient's registration on the study may be canceled. The PI and study coordinator should be notified of treatment delays and/or cancelations as soon as possible.

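### Two hematologic DLT criteria in section 6.2 are first met on day 43 and day 51, after Cycle 1 has ended, yet only Cycle 1 DLTs drive escalation

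*Combined protocol and SAP*

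**What the plan says.** On the window, section 6.1 says "Cycles are to be repeated every 21 days". Section 6.2 opens its list with "DLTs will be defined in Cycle 1 as any of the following events" and ends by restricting escalation decisions to DLTs that arise in Cycle 1. Section 9.3.1 equates the DLT-evaluation period with Cycle 1. It asks for observation over a required duration but gives no day count and no rule for a late or missing Cycle 2.

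The list in section 6.2 includes:

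- "Grade 4 neutropenia or thrombocytopenia extending beyond day 42 in patients with less than 5% blasts in marrow", with further conditions on MDS changes and disease by flow cytometry;
- a late start of Cycle 2, in two forms: "More than 2 week delay due to lack of recovery" (non-hematologic toxicity) and "More than 4 week delay due to lack of recovery" (hematologic toxicity not attributed to leukemic infiltration);
- "Any toxicity that requires discontinuation of either study drug".

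The section then adds: "Note that hematologic toxicities are not DLTs except as noted above".

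On delay, sections 6.7, 7.2.1 and 7.3 each end study treatment when toxicity holds up a new cycle for more than 14 days. None makes a hematologic exception. Section 7.2.1 asks for treatment-related toxicity of grade 1 or lower before a new cycle. Section 7.3 also accepts the patient's baseline, or a level the treating physician finds acceptable after discussion with the principal investigator.

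**The concern.** A DLT criterion is useful in a 3+3 design only if it can be met inside the period whose DLTs are counted. Here two of the listed hematologic criteria appear to lie wholly outside that period. The 3+3 table in section 6.3 turns on single patients: one reclassified case changes 0 of 3 (escalate) to 1 of 3 (enroll at least three more), or 1 of 6 to 2 of 6 (stop). If two sites or reviewers read the window differently, the same patient with prolonged cytopenia can produce different escalation decisions and a different MTD. Section 6.3 does not say how long a cohort must be observed before the next level opens.

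**Working it through.** The plan states no closing day for the DLT window, so there is no figure of its own to reproduce. The enrollment figures in section 9.2 do not depend on this point.

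**Inputs.** Cycle length 21 days (6.1); delay cap 14 days (6.7, 7.2.1, 7.3); thresholds of day 42, more than 2 weeks and more than 4 weeks (6.2).

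**End of Cycle 1.**

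- Cycle 2 is due on day 21 + 1 = 22.
- With no delay, Cycle 1 ends on day 21.
- Under the cap, the latest Cycle 2 start is day 22 + 14 = 36, so Cycle 1 ends by day 35.

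**First day each criterion can be met.** A delay of d days puts the Cycle 2 start on day 22 + d, so a delay of more than d days is first reached on day 22 + d + 1.

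| Criterion in 6.2 | First met | Days after day 21 | Days after day 35 |
|---|---|---|---|
| Non-hematologic delay, more than 14 days | 22 + 15 = day 37 | 16 | 2 |
| Grade 4 cytopenia beyond day 42 | day 43 | 22 | 8 |
| Hematologic delay, more than 28 days | 22 + 29 = day 51 | 30 | 16 |

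Counting the delay from the end of day 21 instead moves the last row to 21 + 29 = day 50, still after day 35.

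**Grade 4 item with Cycle 2 on time.** Suppose a patient starts Cycle 2 on day 22 at a level found acceptable under section 7.3. If Cycle 3 is also on time, day 43 is Cycle 3 Day 1 (2 × 21 + 1 = 43). Cycle 1 has then ended on any reading, so an event on that day cannot have occurred in it. This is the clearest case.

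**Window held open until Cycle 2 starts or treatment stops.** A hematologic delay of 15 to 28 days corresponds to a Cycle 2 start on days 37 to 50. It has not reached the 4-week item, but it has passed the cap, so treatment must stop. The list counts any one of its items, and the discontinuation item is one of them. On that reading the case is a DLT well before day 51, and the 4-week item adds almost nothing. The non-hematologic item causes less trouble: its limit and the cap coincide at more than 14 days, so the two rules agree.

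**The case against.** The strongest reply is that a fixed close at day 21 is the weakest reading of the plan. A list that makes late initiation of Cycle 2 a Cycle 1 DLT implies that Cycle 1 stays open until Cycle 2 begins or treatment ends. On that reading the discontinuation item catches a hematologic delay of more than 14 days, and the redundancy errs toward counting. This largely stands. A reader might infer that a 15-to-28-day hematologic delay escapes the count; the text more naturally counts it. The inference is not closed off, however. The note that hematologic toxicities are DLTs only as listed does not rank the items, and section 6.7 lists the over-14-day delay separately from permanent discontinuation of one drug. Nor does the open window rescue the grade 4 item when Cycle 2 starts on time.

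A reader might also infer that late cytopenia could not affect the RP2D, the primary endpoint. Section 6.4 rules that out: it allows an RP2D below the MTD in view of adverse events that are not DLTs and the frequency of dose modifications. Section 6.2 also monitors toxicity through all cycles.

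Safety follow-up can be extended (6.8), a marrow may be required (6.2), and escalation needs the principal investigator's sign-off with at least monthly calls (13.1). These make a careless decision less likely, but they do not define the window. The growth-factor text in section 6.5 that refers to days 28 to 42 concerns grade 4 neutropenia in Cycle 2 or later and has no bearing here.

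Finally, one bullet just before the DLT definition is redacted, so the claim can only be that no visible passage settles the matter.

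**Conclusion.** The contradiction is real. With DLTs confined to Cycle 1, the grade 4 cytopenia item and the 4-week hematologic delay item come 22 and 30 days after an undelayed Cycle 1, and 8 and 16 days after one stretched to the cap. Taken literally, they are inoperative in the 3+3 rule. On the more natural open-window reading, the 4-week item becomes nearly redundant, and the grade 4 item still fails for a patient who goes on to Cycle 2 on time. That is a faulty rule, not merely a missing detail.

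The consequence is limited to cohort-to-cohort escalation and the MTD. No probability of a wrong escalation can be given. The documents state no rate for prolonged grade 4 cytopenia, and that item applies only to patients with under 5% marrow blasts and the added conditions on residual disease. Section 2.3 reports anemia and neutropenia with both drugs and calls them generally acceptable in this population; that says nothing about how often the late criteria would be reached. The conclusion rests on the day counts and the visible wording alone.

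**What to change.** Reconcile sections 6.2, 6.7, 7.2.1, 7.3 and 9.3.1:

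1. In 9.3.1, state the day or event that closes the DLT-evaluation period when Cycle 2 is delayed or never starts, so that every criterion kept in 6.2 can be met within it.
2. In 6.2, state which item governs when the discontinuation item and a specific delay item both apply.
3. Bring the closing sentence of 6.2 on Cycle 1 DLTs, the blood-count schedule in section 11 and the timing of the escalation decision in 6.3 into line with that period.

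Which clinical limits stand is for the sponsor; the need is that they agree.

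The cost is wording, some extra blood counts and occasional waiting. A cohort with an unresolved case might be held to about day 37, 43 or 51, depending on the limits kept. That is 16, 22 or 30 days past day 21, or about 2 to 4 weeks. Escalation is sequential, so later cohorts would wait too.
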